2.1.1.11 Windows for multiple assessments

For the definition of time windows for visits please refer to the study protocol, [[Tables 8-3](#)] and [[Table 8-4](#)]. Variations of ± 1 week in the visits schedule are allowed.

Time windows will be defined for descriptive summary of PRO data by visit and longitudinal data analysis. If more than one assessment is available in the same time window, the assessment closest to the planned date will be considered. If two assessments are obtained equidistant compared to the scheduled visit day, the assessment obtained prior to visit will be considered.

Table 2.1-1 Time Window for PROs

Time Window	Planned Visit Timing	Time Window Definition
On treatment		
Baseline	On or before Study Day 1*	\leq Study Day 1*
Week 12	Study Day 78	Study Days 2 – 120
Week 24	Study Day 162	Study Days 121 – 204
Week 36	Study Day 246	Study Days 205 – 288
Every 12 weeks thereafter		
Week 12^*k ($k = 4, 5, \dots$)	$d = 7^*(12^*k-1)+1$	Study Days $d-41$ to $d+42$ Note: window for last visit before EOT: $d-41$ to EOT date-1

End of treatment during randomized treatment period

End of treatment	N.A.	Data collected under EOT visit
* Study Day 1 = randomization date		

Data from all assessments (scheduled and unscheduled), including multiple assessments, will be listed.

Last contact date

The last contact date will be derived for patients not known to have died at the analysis cut-off using the last complete date among the following:

Table 2.1-2 Last contact date data sources

Source data	Conditions
Date of Randomization	No Condition
Last contact date/last date patient was known to be alive from Visit Form 3	Patient status is reported to be alive
Start/End* dates from drug administration record	Non-missing dose. Doses of 0 are allowed.
End of treatment date from end of treatment page	No condition.
Date of PRO assessment	At least one non-missing answer to questionnaire
Tumor (RECIST) assessment date	For non-target lesion: non-missing lesion status; For target lesion: non-missing lesion diameter; For new lesion: "Is there a new lesion?" = yes
Laboratory/PK collection date	Sample collection marked as 'done'.
Vital signs and ECG date	At least one non-missing parameter value
Performance Status date	Non-missing performance status
Start/End dates of AE	Non-missing verbatim term
Concomitant medication/Non-drug therapy date	Non-missing medication
Physical exams	At least one non-missing value

The last contact date is defined as the latest complete date from the above list. The cut-off date will not be used for last contact date, unless the patient was seen or contacted on that date. No date post cut-off date will be used. Completely imputed dates (e.g., the analysis cut-off date programmatically imputed to replace the missing end date of a dose administration record) will not be used to derive the last contact date. Partial date imputation is allowed to derive the last contact date to estimate death or censoring coming from the death form or end of study eCRF, respectively, and these rules are summarized in [Section 5.1.2.1](#).

The last contact date will be used for censoring of patients in the analysis of overall survival.

2.2 Analysis sets

Full Analysis Set

The Full Analysis Set (FAS) comprises all patients to whom study treatment has been assigned by randomization. According to the intent to treat (ITT) principle, patients will be analyzed according to the treatment and strata, they have been assigned to during the randomization procedure. The FAS will be the primary population for all efficacy analyses.

Safety set

The Safety set (SAF) includes all subjects who received at least one dose of study treatment. Patients will be analyzed according to the study treatment received, where treatment received is defined as the randomized treatment if the subject took at least one dose of that treatment or the first treatment received if the randomized/assigned treatment was never received. So, if a patient randomized to the Lutathera arm receives only Octreotide, that patient will be counted as an Octreotide arm patient as far as safety is concerned. Likewise, if a patient randomized to the Octreotide arm receives Lutathera instead, that patient counts as a Lutathera patient.

Cross-over set

The cross-over set is comprised of all patients randomized to the Sandostatin® LAR Depot (octreotide long-acting) arm who received at least one cross-over dose of Lutathera® (¹⁷⁷Lu-DOTA⁰-Tyr³-Octreotate) following confirmed disease progression per BIRC in the randomized period.

Re-treatment set

The re-treatment set is comprised of all patients randomized to the Lutathera® (¹⁷⁷Lu-DOTA⁰-Tyr³-Octreotate) arm who received at least one re-treatment dose of Lutathera® (¹⁷⁷Lu-DOTA⁰-Tyr³-Octreotate) after confirmed disease progression per BIRC in the randomized period.

Pharmacokinetic analysis set (PAS)

The Pharmacokinetic analysis set (PAS) includes all subjects who provide at least one evaluable PK concentration at baseline and post-dose.

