	22. Other known co-existing malignancies except non-melanoma skin cancer and carcinoma in situ of the uterine cervix, unless definitively treated and proven no evidence of recurrence for 5 years.
	23. Patient with known incompatibility to CT Scans with I.V. contrast due to allergic reaction or renal insufficiency. If such a patient can be imaged with MRI, then the patient would not be excluded.
	24. Hypersensitivity to any somatostatin analogues, to the IMPs active substance or to any of the excipients.
	25. Patients who have participated in any therapeutic clinical study/received any investigational agent within the last 30 days.
Study treatment	In this study, approximately 222 patients with advanced G2-3 GEP-NET will be randomized (2:1 randomization ratio) to receive treatment with Lutathera (7.4 GBq or 200 mCi x 4 administrations every 8 ± 1 weeks; cumulative dose: 29.6 GBq or 800 mCi) plus octreotide long-acting standard dose (30 mg every 8 weeks during Lutathera treatment and every 4 weeks after last Lutathera treatment) or octreotide long-acting high dose (60 mg every 4 weeks).
	The investigational drug product Lutathera [®] (¹⁷⁷ Lu-DOTA ⁰ -Tyr ³ - Octreotate) will be provided by the Sponsor. The Sponsor will also provide the 2.5% Lys-Arg sterile amino acid solution for infusion (if it can't be compounded at the hospital Pharmacy), as well as octreotide long-acting (Sandostatin [®] LAR Depot) for the entire duration of the Treatment Phase (and optional Treatment Extension Phase in case of cross-over) of the study. During the re-treatment period, Lutathera [®] and 2.5% Lys-Arg sterile amino acid solution for infusion (if it can't be compounded at the hospital Pharmacy) will be provided by the Sponsor. Patients will switch to prescribed drugs in the follow up phase.
	Anti-emetics, SRI imaging agents, short-acting octreotide or any other supportive care medication will not be supplied by the Sponsor.
Efficacy assessments	During the Treatment Phase, objective tumor response will be assessed at W16 \pm 1, W24 \pm 1 and then every 12 \pm 1 weeks from the randomization date, according to RECIST 1.1 criteria (central + local assessment up to first progression, then only local assessment). During the Follow up Phase RECIST objective tumor response will be assessed locally (scans every 6 months).

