In addition, patients randomized in the control arm have the option, if eligible, to enroll for postprogression cross-over with Lutathera, see Table 8-4). Control arm patients who cross-over after progression will be allowed to complete the Lutathera treatments after week 72 or to cross-over during the Follow-up Phase, in case of late progression. Furthermore, patients who experience disease progression in the Lutathera arm have the option, if eligible, to enroll for re-treatment phase with Lutathera, see Table 8-3.

Patients included in the optional crossover or re-treatment phase will be followed up at least 6 months and up to 3 years (or until EoS, whatever comes first).

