5.2.1 Eligibility Criteria for Optional Treatment Extension Phase (cross-over)

Any centrally confirmed RECIST progressive patient has the option to enroll for post-progression cross-over and receive maximum 4 cycles of Lutathera (7.4 GBq/200 mCi x 4 cycles; cumulative dose: 29.6 GBq / 800mCi) plus octreotide long-acting (30 mg every 8 weeks), provided that the following criteria are met:

- Patients have provided a signed informed consent form to participate in the study treatment extension phase, obtained prior to the start of any related procedures.
- Expression of somatostatin receptors on all target lesions (based on post-progression new baseline assessment) documented by CT/MRI scans (Note: Cross-over Eligibility CT/MRI scan doesn't need to be repeated if performed within the previous 12 weeks), assessed by any of the following somatostatin receptor imaging (SRI) modalities within 3 months prior to Lutathera treatment: [68Ga]-DOTA-TOC (e.g. Somakit-TOC[®]) PET/CT imaging (or MRI when applicable based on target lesions), [68Ga]-DOTA-TATE PET/CT (or MRI when applicable based on target lesions) imaging (e.g. NETSPOT[®]), Somatostatin Receptor scintigraphy (SRS) with [111In]-pentetreotide (Octreoscan[®] SPECT/CT), SRS with [99mTc]-Tektrotyd, [64Cu]-DOTA-TATE PET/CT imaging (or MRI when applicable based on target lesions).
- All protocol inclusion/exclusion criteria are met (see Sections 5.1 and 5.2).
- The time window to start cross-over is 4 years after last patient randomized.
- Note: Prior each Lutathera administration a 6-week washout period from last octreotide long-acting administration has to be applied.

If RECIST progression occurs after Week 72 post the primary end point analysis, the decision to enroll the patient in cross-over will be based on local assessment.

Images (Cross-over Eligibility SRI and CT or MRI scan) will be also submitted to the central imaging center for a second review: there is no central 'real time' assessment of the Cross-Over Eligibility SRI uptake; however, the images should be submitted to the central imaging center possibly within 1 month. Images submission is not required for screening failure patients.

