5.2.2 Eligibility Criteria for Optional Re-Treatment Phase

In the Lutathera arm, patients with radiological progression based on RECIST criteria in central assessment, have the option to enroll for post-progression re-treatment, upon signature of a new informed consent, to receive 2 to 4 additional cycles of 7.4 GBq/200 mCi of Lutathera.

For enrolment in the optional re-treatment phase, patients must meet all following requirements:

- Randomized to Lutathera arm, received 4 doses of Lutathera in initial treatment and experienced either disease stabilization (SD) or objective response (PR/CR) (centrally confirmed) for at least 6 months after the 4th Lutathera dose. If a patient's response has changed from PR/CR to SD within 6 months after the 4th Lutathera dose, the patient is still eligible for re-treatment, provided there is no documented progression within 6 months. A window of -2 weeks is allowed for the confirmation of 6 months of SD/PR/CR response.
- Lutathera was overall well tolerated; no recorded SAEs related to Lutathera that were not resolved before the next Lutathera dose and led to treatment interruption.
- After the SD/PR/CR response, experienced radiological RECIST progression (centrally confirmed). If RECIST progression occurs after Week 72 post the primary end point analysis, the decision to enroll the patient in re-treatment will be based on local assessment.
- Patient did not receive any other systemic treatment for GEP-NET after progression (somatostatin analogues are allowed).

- Investigator's agreement that re-treatment is in the best interest for the patient
- Patients have provided a signed informed consent form to participate in the re-treatment phase, obtained prior to the start of any related procedures.
- Time window to start re-treatment: 4 years after last patient randomized (see Section 9.2).

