12.1 Analysis sets

The Full Analysis Set (FAS) comprises all subjects to whom study treatment has been assigned by randomization. According to the intent to treat principle, subjects will be analyzed according to the treatment and strata they have been assigned to during the randomization procedure.

The Safety Set includes all subjects who received at least one dose of study treatment. Patients will be analyzed according to the study treatment received, where treatment received is defined as the randomized treatment if the subject took at least one dose of that treatment or the first treatment received if the randomized/assigned treatment was never received.

The pharmacokinetic analysis set (PAS) consists of all randomized patients who received at least one dose of study drug and had at least one post dosing evaluable PK assessment.

The cross-over set is comprised of all patients randomized to the Sandostatin LAR Depot (octreotide long-acting) arm who received at least one dose of Lutathera after cross-over following confirmed disease progression per central, blinded, real-time images reading in the randomized period.

The re-treatment set is comprised of all patients randomized to the Lutathera arm who received at least one dose of Lutathera during re-treatment period after confirmed disease progression per central, blinded, real-time images reading in the randomized period.

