2.1.1.9 Definition of study phases

Randomized Treatment Phase

The randomized treatment phase starts on the randomization date and ends at the end of treatment date filled on the end of treatment CRF page (For EOT during treatment phase).

Extension Treatment Phase

For the control arm patients going into the cross-over period and receiving Lutathera treatment, the cross-over phase starts at the date of 1st treatment with Lutathera and ends at the end of treatment date filled on the end of treatment cross-over CRF page.

For the investigational arm patients going into the re-treatment period, the re-treatment period starts at the date of 1st re-treatment with Lutathera and ends at the end of treatment date filled on the end of treatment re-treatment page.

Follow-up Phase

The Follow-up phase starts one day after the end of treatment phase/extension phase (whichever was the last phase that the patient completed) and ends at the end of study date filled on the end of study CRF Page.

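### The cross-over and re-treatment sets require central progression in the randomized period, so patients correctly enrolled late on local progression fall outside them

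*SAP*

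**What the plan says.** **Set definitions.** SAP 2.2 limits the cross-over set to control-arm patients with at least one cross-over dose of Lutathera "following confirmed disease progression per BIRC in the randomized period". It limits the re-treatment set to Lutathera-arm patients with at least one re-treatment dose "after confirmed disease progression per BIRC in the randomized period". Protocol 12.1 uses the same condition, worded for cross-over as "following confirmed disease progression per central, blinded, real-time images reading in the randomized period". Each definition therefore asks for two things beyond a dose: central confirmation, and progression in the randomized period.

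**Entry rules.** Entry is normally on central assessment. When progression comes after Week 72 following the primary analysis, protocol 5.2.1 says "the decision to enroll the patient in cross-over will be based on local assessment" and 5.2.2 says "the decision to enroll the patient in re-treatment will be based on local assessment". Sections 3.3 and 3.4 carry the same rule, and footnote 4 to SAP Figure 1.1-1 repeats it for re-treatment. Protocol 3.2 also allows control-arm patients "to cross-over during the Follow-up Phase, in case of late progression".

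**Reading of scans.** The protocol synopsis, under efficacy assessments, states: "During the Follow up Phase RECIST objective tumor response will be assessed locally". SAP 2.1.1.9 says that the randomized treatment phase "ends at the end of treatment date filled on the end of treatment CRF page".

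**The concern.** The plan creates a route into the extension phases that its own set definitions do not recognise. A patient who progresses late, is judged progressive locally as the protocol directs, signs the new consent and receives Lutathera has followed every rule, and is still not a member of the set named for that phase.

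The omission is not random. The patients left out are those with the longest time to first progression in their arm. A cross-over PFS curve run on the remaining patients describes earlier progressors only, and the set counts understate how many patients received cross-over or re-treatment. The documents do not allow the direction of any resulting bias to be predicted.

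**Working it through.** **1. Does a compliant late entrant meet the definition?**

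- *Central confirmation.* Protocol 8.3.1 runs central reading to the primary analysis and then to Week 72 after randomization. Follow-up scans are read locally. A patient admitted under the local rule need have no central progression.
- *In the randomized period.* The SAP does not define this exact term. The nearest definitions are the randomized treatment phase (2.1.1.9, ending at the end-of-treatment date) and the randomized treatment period (2.1.1.10, ending no later than 30 days after the last randomized dose). A progression found later in follow-up is outside both.

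Such a patient can fail both conditions. SAP Table 2.2-1 does not repair this: for these two sets it lists only a missing phase-specific consent as a reason for exclusion. SAP 2.5.3 and Table 2.5-1 (row G) already foresee cross-over or re-treatment before a central PFS event, so the SAP does not itself treat central progression as universal among these patients.

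**2. Which outputs use the sets?**

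- Tied to a set: the counts per analysis set (SAP 2.3.1) and the investigator-assessed cross-over PFS (SAP 2.5.6), which is run only if events allow.
- Not tied to a set: the cross-over and re-treatment periods (SAP 2.1.1.10, by dosing dates); safety by phase or period (2.8 and 2.8.1); long-term AESIs (2.8.1.1, by receipt of Lutathera); re-treatment ORR, PFS, DCR and DOR (2.7.1, by receipt); re-treatment safety in protocol 12.6.4 (by receipt).

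**3. How many patients could be involved?**

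Inputs from SAP section 3 and protocol 12.8.1: HR 0.50, medians 15 and 30 months, one-sided 2.5%, 90% power, 74 control and 148 Lutathera patients, uniform accrual over 22.2 months, 15% dropout, primary analysis at month 35. The entry window closes 4 years after the last randomization: 22.2 + 48 = month 70.2.

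The plan's own figures first:

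- Events = (1.960 + 1.282)² / [(2/3)(1/3)(ln 0.5)²] = 10.51 / 0.1068 = 98.4, so 99, as stated. Power at 99 events is 90.2%.
- Critical HR = exp(−1.96/√(99 × 2/9)) = exp(−1.96/√22) = 0.658, as stated.

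Projection, with exponential PFS: λ = ln 2/15 = 0.0462 (control) and ln 2/30 = 0.0231 (Lutathera) per month. The dropout hazard η = 0.00994 per month gives 15% dropout by month 35. It is assumed equal in both arms and constant afterwards. Expected events at month 35 are 99.4, which matches the plan.

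For entry time a, averaged over 0 to 22.2 months, expected events in an arm of n patients are

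n × mean of λ/(λ+η) × [exp(−(λ+η)·lo) − exp(−(λ+η)·hi)], with hi = 70.2 − a.

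Seventy-two weeks is 72 × 7/30.4375 = 16.6 months. The Week 72 rule can be read in two ways:

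- Reading A: after the primary analysis and more than 72 weeks from randomization; lo = max(35 − a, 16.6).
- Reading B: more than 72 weeks after the primary analysis; lo = 35 + 16.6 − a = 51.6 − a.

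| | All PFS events to month 70.2 | Reading A | Reading B |
|---|---|---|---|
| Control, 15% dropout | 58.6 | 14.2 (24%) | 4.3 (7%) |
| Lutathera, 15% dropout | 88.5 | 32.4 (37%) | 12.8 (14%) |
| Control, no dropout | 69.0 | 20.0 | 6.9 |
| Lutathera, no dropout | 109.8 | 47.2 | 20.6 |

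The no-dropout rows keep the primary analysis at month 35.

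**The case against.** The strongest reply is that very little output depends on these sets. A reader might infer that late entrants vanish from the safety tables and that re-treatment efficacy is biased. The documents do not support that: those summaries are defined by dosing period or receipt of Lutathera, all AEs are listed and flagged by period, and the patients remain in the FAS and Safety Set. What is left is a set count and one optional, single-group, descriptive curve. This part of the reply stands.

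It can also be said that the intent is visible, since Table 2.2-1 gives no sign that locally qualified patients are to be removed, and that eligibility CT/MRI scans still go to the central imaging center for a second review. Neither point closes the gap. Table 2.2-1 does not override the definition. The second review is not stated to confirm progression for set membership, and it would not place the progression in the randomized period.

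One risk remains on the safety side. SAP 2.8 names the safety set for the treatment phase but no set for the extension phases. A programmer could take the cross-over and re-treatment sets as denominators there; the SAP neither requires nor rules this out.

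**Conclusion.** The contradiction is real and appears in both documents. As written, it gives the wrong population for the analysis-set counts and for the cross-over PFS. Other extension-phase summaries are affected only if the sets are used as denominators. No confirmatory result is touched: the local rule starts after the primary analysis, and SAP 2.1.1.10 defers extension-period efficacy beyond it.

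With the planned dropout, at most about 4 to 14 control-arm and 13 to 32 Lutathera-arm PFS events fall under the local rule. They are ceilings on late entrants under that model, because PFS events include deaths and the documents give no eligibility or uptake rates. They rest on exponential PFS at the planned medians and a constant dropout hazard; without dropout the ranges are 7 to 20 and 21 to 47.

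A reader might instead subtract 99 events and 15% dropout (about 33) from 222 and infer that about 90 patients are at stake. That counts everyone event-free and still followed at the primary analysis. It includes patients who progress while central reading continues, those who die, and those who do not progress before the window closes.

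**What to change.** In SAP 2.2 and protocol 12.1:

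- Define each set as patients of the relevant arm who received at least one cross-over (or re-treatment) dose of Lutathera after progression qualifying under the protocol's entry rule: central, or local when late.
- Delete the condition that progression falls in the randomized period.
- Record the basis of progression (central or local) as a descriptor, so that results can be shown by it.
- In the SAP, name the set used for each extension-phase summary.

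The two readings of Week 72 should also be reconciled in the text, since they decide who counts as late.

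The cost is one phrase in each of two definitions in each document, plus a line per summary. No design figure changes: events stay at 99, N at 222 and power at 90%. The change can be made before the final analysis. If only the SAP is amended, its section 4, which now reports no change to protocol-specified analyses, should record the difference.

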8.6 Pharmacokinetics

This section is applicable to all countries, except for China. No PK samples will be collected in China.

The steady-state plasma concentrations of high dose octreotide long-acting will be assessed in the control arm of the study.

All samples will be taken by either direct venipuncture or indwelling cannula inserted in a forearm vein. Blood samples (2.5 mL each sample) will be collected to yield approximately 1 mL plasma for analysis of octreotide concentration. Immediately after blood is drawn into K3EDTA tubes, they should be inverted gently several times to ensure the mixing of tube contents. Prolonged exposure to rubber stopper should be avoided. The tube should be placed upright in tube rack surrounded by ice until centrifugation. Within 20 minutes, the sample should be centrifuged between 3°C and 5°C for 10 minutes at approximately 1000 x g. Immediately after centrifugation, 1.0 mL plasma should be transferred to a polypropylene screw-cap tube immersed in dry ice. The storage temperature for PK samples should be at or below minus 20°C (-20°C). The samples will be sent to an external laboratory for central assessment (see further details in the PK Manual).

		CONTROL A	ARM	
Sample	Volume (mL)	Week	PK Collection #	Scheduled time (h)
Blood	2.5	4	1	0 (pre-dose)*
Blood	2.5	12	2	0 (pre-dose)*
Blood	2.5	16	3	0 (pre-dose)*
Blood	2.5	24	4	0 (pre-dose)*
*Blood sampl	e for PK must be col	lected before oc	treotide long-acting	; injection.

Table 8-5. Octreotide long-acting PK blood collection plan

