12.6.3 Pharmacokinetics

Patients in the control arm (all countries except for China) will yield PK data from blood sampling performed at pre-dose with respect to the octreotide long-acting i.m. injection for the 2nd, 4th, 5th and 7th treatment cycle (that is respectively at week 4, 12, 16 and 24) for the determination of plasma trough levels. Data will be processed using a population based model, for exploratory purposes. More details on the presentation of results will be given in the SAP.

Additionally, descriptive statistics and graphical display of octreotide plasma concentrations during the course of treatment will presented by dose group. Exploratory analysis will be performed to assess the dose-exposure relationship. More details on the presentation of results will be given in the SAP.

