2.1.1.8 Baseline

For efficacy evaluations, the last non-missing assessment, including unscheduled assessments on or before the date of randomization is taken as “baseline” value or “baseline” assessment. In the context of baseline definition, the efficacy evaluations also include PRO.

For safety evaluations (e.g., laboratory assessments, ECGs, and vital signs), the last available assessment, including unscheduled assessments, on or before the start of study treatment as described in [Section 2.1.1.4](#) will be used as the “baseline” assessment. Assessments specified to be collected post-dose on the 1st date of treatment are not considered as baseline values.

If participants have no value as defined above, the baseline results will be considered missing.

Since study treatment in the randomized treatment phase can still potentially contribute to the safety profile in the cross-over and re-treatment phase, therefore, for cross-over and re-treatment analyses, baseline for safety analysis is the same as defined above, i.e., last available assessment on or before the start of study treatment.

For efficacy evaluations of the cross-over and re-treatment period, the last available assessment on or before first cross over treatment/re-treatment with Lutathera® is regarded as “baseline” for the assessments.

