2.2.1 Participant classification

Patients may be excluded from the analysis populations defined above based on the protocol deviations entered in the database and/or on specific subject classification rules defined in [Table 2.2-1](#).

Table 2.2-1 Subject classification based on protocol deviations and non-PD criteria

Analysis set	Protocol deviations leading to exclusion	Non protocol deviation leading to exclusion
--------------	--	---

FAS	No written informed consent	Not applicable
Safety set	No written informed consent	No dose of study medication
Cross-over Set	Cross-over specific ICF not completed	Not applicable
Re-treatment Set	Re-treatment specific ICF not completed	Not applicable
PK Analysis Set	No written informed consent	No evaluable PK concentration at baseline or post-dose.

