2.9 Pharmacokinetic analysis

PK assessments:

Patients in the control arm will yield PK data from blood sampling performed at pre-dose with respect to the octreotide long-acting i.m. injection at week 4, 12, 16 and 24 for the determination of plasma trough levels. These trough levels will be presented descriptively.

Descriptive statistics regarding trough levels of octreotide (n, arithmetic mean, CV% mean, standard deviation (SD), median, minimum and maximum) will be presented for Pharmacokinetic analysis set. Since patients in the control arm can start on a lower dose than that specified for the control arm (60 mg), descriptive statistics will be presented for those who start below 60 mg, those that start at 60 mg, and overall.

In addition, the arithmetic/geometric mean (\pm SD) and median concentration-time profiles over time will be displayed graphically on the linear and semi-log view.

All individual trough levels will be listed using the Full analysis set.

The above PK summary will be generated separately, but not be included in the primary CSR.

PK parameters

Not applicable. No PK parameters will be derived.

Handling of PK data below LLOQ or missing

All concentration values below the lower limit of quantitation (LLOQ) are set to zero by the Bioanalyst, and will be displayed in the listings as zero and flagged. LLOQ values will be treated as zero in any calculations of summary statistics. The number of non-zero concentrations will also be reported in the summary statistics.

Missing values for any PK data will not be imputed and will be treated as missing.

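### The SAP's PK analysis set requires a baseline concentration that is never scheduled, so read literally the set is empty; Table 2.2-1 and protocol 12.1 say something different

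*SAP*

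**What the plan says.** SAP 2.2 defines the pharmacokinetic analysis set as one that "includes all subjects who provide at least one evaluable PK concentration at baseline and post-dose". Table 2.2-1 in SAP 2.2.1 gives the matching non-deviation reason for exclusion as "No evaluable PK concentration at baseline or post-dose".

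Protocol 12.1 defines the same set differently: randomized patients who "received at least one dose of study drug and had at least one post dosing evaluable PK assessment". It has no baseline condition. SAP Section 4, which should record departures from the protocol's analyses, is marked not applicable.

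The sampling schedule is the same wherever it appears (protocol synopsis, Table 8-4, Table 8-5, protocol 12.6.3, SAP 2.9). Blood is drawn in the control arm only, at Weeks 4, 12, 16 and 24. Protocol 12.6.3 describes the sampling as "performed at pre-dose with respect to the octreotide long-acting i.m. injection for the 2nd, 4th, 5th and 7th treatment cycle". Protocol 8.6 adds that "No PK samples will be collected in China".

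SAP 2.1.1.8 has no PK-specific baseline. For safety evaluations, baseline is "the last available assessment, including unscheduled assessments, on or before the start of study treatment"; for efficacy evaluations it is fixed at or before randomization.

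**The concern.** The analysis-set definition asks for a sample that the trial does not plan to take. A programmer who applies SAP 2.2 as written, with the SAP's own meaning of baseline, finds no eligible patient. One who works from Table 2.2-1 may find none or almost all of the sampled patients, depending on how the 'or' is read. Neither wording matches the protocol, and the difference is not declared.

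At stake is the descriptive trough summary in SAP 2.9, which is presented on this set for patients starting below 60 mg, for those starting at 60 mg, and overall. Steady-state trough concentration is the only endpoint listed for the exploratory objective on the PK of the 60 mg dose.

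**Working it through.** **Inputs**
- Sampling weeks 4, 12, 16 and 24: protocol Table 8-5 and 12.6.3, SAP 2.9.
- First injection at Week 0, then every 4 weeks: protocol Table 8-4.
- Planned control arm of 74, an upper bound on those sampled because China is excluded: protocol 12.8.1.
- Baseline on or before the start of treatment (safety) or randomization (efficacy): SAP 2.1.1.8.

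**Check of the schedule.** Cycle = week/4 + 1 gives 4/4 + 1 = 2, 12/4 + 1 = 4, 16/4 + 1 = 5 and 24/4 + 1 = 7. These are the cycles stated in protocol 12.6.3. Cycle 1 (Week 0) is not sampled.

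**Classifying the 4 scheduled samples per patient**
- On or before the first dose: 0 of 4.
- After the first dose: 4 of 4.
- Labelled pre-dose relative to the injection at that visit: 4 of 4.

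**Applying each rule to the control arm**, best case, with every scheduled sample taken and evaluable:

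| Rule | Baseline sample needed? | Patients kept, of at most 74 |
|---|---|---|
| SAP 2.2, both required | yes | 0 |
| Table 2.2-1, excluded if either is missing | yes | 0 |
| Table 2.2-1, excluded only if there is neither | no | up to 74 |
| Protocol 12.1 | no | up to 74 |

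The choice between the safety and efficacy baselines does not matter, since neither is met by any scheduled sample.

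Reading both terms relative to each visit's own injection does not help either. All 4 samples are then pre-dose and none is post-dose, so the requirement for both still fails. Treating a later pre-injection trough as baseline rescues the rule only if 'post-dose' is counted from the first injection, that is, if the two words use different reference points.

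**Outputs affected.** If the three groups in SAP 2.9 are each summarized at the four sampling weeks, 3 × 4 = 12 summary cells depend on this set. SAP 2.9 names the groups and the statistics; the by-week layout is my assumption.

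**The case against.** The best counter-argument is that the SAP can be read sensibly. SAP 2.1.1.8 does not name PK, so importing its baseline into SAP 2.2 is an inference. The SAP 2.2 wording could mean at least one concentration across the two times, not one at each. In ordinary English, the Table 2.2-1 exclusion means no concentration at either time, and SAP 2.2.1 presents that table as the source of the classification rules. Read that way, the table selects the same patients as protocol 12.1, because no baseline samples exist. An unscheduled pre-treatment sample is also conceivable.

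Much of this is fair. A competent programmer would probably reach the intended population, and an empty set would be obvious as soon as the output was run, so it could not bias a result unnoticed. But each of these routes replaces the rule in SAP 2.2 with one it does not state, and the SAP does not say which should prevail. A set made up of patients who happened to have an unplanned pre-treatment sample would not be the intended population either.

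The objection on importance also stands. The set serves one exploratory, descriptive, control-arm summary, about which SAP 2.9 says "The above PK summary will be generated separately, but not be included in the primary CSR". SAP 2.9 also states "All individual trough levels will be listed using the Full analysis set", so no concentration goes unreported.

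**Conclusion.** The definition in SAP 2.2 is wrong as written, at minor severity. Followed literally, with baseline as in SAP 2.1.1.8 and scheduled samples only, it admits 0 of up to 74 control patients; under protocol 12.1, every sampled patient with an evaluable trough enters. Table 2.2-1 does not settle the matter, since its two readings give 0 and up to 74. SAP 2.2 also omits the protocol's explicit condition of at least one dose, and Section 4 does not declare the change. No primary, key secondary or safety analysis uses this set.

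**What to change.** Return SAP 2.2 to the intent of protocol 12.1: all randomized patients who received at least one dose of study drug and have at least one evaluable octreotide concentration from a sample taken after their first octreotide long-acting injection. Change the Table 2.2-1 entry to exclude patients with no evaluable concentration after that first injection.

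Name the first injection explicitly and do not rely on 'post-dose' alone, because every scheduled sample is labelled pre-dose for its own visit. This is slightly more specific than the wording of protocol 12.1, but it selects the patients the protocol intends.

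The cost is two lines of SAP text, best made before database lock. No new data are needed, and sample size and alpha are untouched. Section 4 can then stay as it is for this item. If a baseline sample really was meant to be required, the change should instead be declared and justified in Section 4, together with the source of that sample.
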